Among the oral medications, anti-epileptic drugs such as gabapentin may cause significant side effect (i.e drowsiness) at a higher dose, which prevents its widespread use. As such, combination of vitamins and alpha lipoic acid are becoming more preferred due to its lower rate of side effects. We seek to determine the efficacy of Bionerv, which is an oral combination of alpha lipoic acid (300mg), methylcobalamin (500mcg), Vitamin B1 (39mg) and Vitamin B6 (8mg) on mild to moderate CTS.

5. Research Question(s)

- a. What are the socio-demographic profiles of patients with CTS in Malaysia?
- b. Are oral combination of alpha lipoic acid and vitamin B preparations for the treatment of CTS safe?
- c. Does oral administration of a combination of alpha lipoic acid and vitamin B preparations improve symptoms of CTS?
- d. Does oral administration of a combination of alpha lipoic acid and vitamin B preparations improve electrodiagnostic tests in patients with CTS?

6. Research objectives and hypotheses

General objective

a. To determine the oral efficacy of a combination of alpha lipoic acid and vitamin B preparations in treatment of mild to moderate CTS.

Specific objectives

- a. To describe the socio-demographic profile of patients with mild to moderate CTS in Malaysia.
- b. To examine the efficacy of oral combination of alpha lipoic acid and vitamin B in reducing symptoms of mild to moderate CTS.
- c. To determine if treatment with of oral combination of alpha lipoic acid and vitamin B is associated with improvement of NCS in patients with mild to moderate CTS.

d. To evaluate tolerability of oral combination of alpha lipoic acid and vitamin B in patients with mild to moderate CTS

7. Literature review

CTS is due to local compression of the median nerve, causing conduction blocks within large myelinated nerve fibers. It reduces capillary blood flow to the median nerve through the swelling of the synovial tissue of the tendon, commonly at the level of the wrist (4). The reduction of blood flow in the endoneural capillary system then induces alteration in the nerve structure that is provoked by endoneural edema, venous congestion, ischemia, and subsequent metabolic abnormalities (5). It has been proposed that ischemia/reperfusion injury of the median nerve results in oxidative stress and inflammation of the subsynovial connective tissue, which play an important role in the evolution of idiopathic CTS.

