During visit 1, a thorough history and physical examination were done, and demographic data was collected. Afterward, the patients were required to answer three sets of selfadministered questionnaires: Boston Carpal Tunnel Questionnaire (BCTQ), Visual analogue score (VAS) and SF-36. The BCTQ is a specific questionnaire for assessing CTS that consists of two distinct scales, the Symptom Specific Scale (SSS) which has 11 items and the Functional Status Scale (FSS) containing 8 items. Each scale generates a final score ranging from 1 to 5, with a higher score indicating greater disability and poor symptoms control. BCTQ is a reliable questionnaire to assess CTS owing to its high cross-cultural adaptation and multilingual validity and reliability (17-18). The VAS is a visual scale with 0 scored as "no pain" and 10 as "worst pain imaginable" and serves as an excellent tool for pain score with excellent validity and reproducibility (19-20). The SF-36 is a quality-of-life questionnaire that comprises of 36 questions covering eight domains of health which are; Physical Functioning (PF), Role Limitations due to Physical Health, Role Limitations (RL) due to Emotional Problems (RE), energy/fatigue, emotional well-being, social functioning, pain, and general health (GH) where a higher score indicates a better outcome (21). After the administration of these questionnaires, they will be subjected for a nerve conduction study (NCS) to determine the severity of CTS. The NCS were performed by the same trained personnel to ensure consistency and accuracy. A Patient-Reported Questionnaire to monitor any side effects were used to assess the tolerability of the drugs.

The patients were reassessed at Visit 2 (3 months post-treatment) and Visit 3 (6 months post-treatment). During each visit, they underwent physical examination, NCS, and were required to complete the three sets of questionnaires (BCTQ, VAS, and SF-36). They were also required to fill in the form regarding the side effects of the treatments. The investigators made a phone call and sent reminder message at the 6th and 18th week to ensure compliance, medication adequacy and follow up review. During the study, patients were allowed to undergo the standard of care treatment at our center such as physiotherapy.

Fig. 1 The visual analogue scale (VAS).

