Privacy of patients are obtained in a respectful manner whereby every patient is given the confidence to directly disclose information to the researcher in a peaceful and non-threatening manner. Data collection sheets and questionnaires will not contain patients identification such as name, IC number, phone number, address or RN. Specific ID was used on the data collection sheet to ensure patient privacy.

All information obtained in this study will be kept and handled in confidential manner, in accordance to applicable laws and regulations of the country. Data management will be conducted using appropriate database and validation programmes, with standard practice to secure information for all computer based data storage (i.e encryption and password protection). Data collected may be retained for re-use in further studies. The standard duration of three to five years with strict security of research records will be adhered and destroyed after this period of time. Relevant bodies such as JKEUPM will have access to the study data.

Study flowchart

10. Data analysis

Analyses sets

All randomised subjects will be included in the analysis.

Baseline Comparability

True randomisation, concealed location and adequate sample size planned for this study will ensure enough baseline comparability between groups (treatment and control group). Additionally, a table of baseline characteristics of participants in each group, without betweengroup statistical comparisons will be included. This data will be analysed to determine whether any characteristics were imbalanced enough to have influenced the outcomes of the study

Efficacy Analysis

Analyses were performed on an intention-to-treat basis. The primary treatment comparisons of benefit include all eligible patients. Both eligible and ineligible patients are included in the analyses and compared by treatment assignment when an intent-to-treat analysis is specifically indicated.

Safety Analysis

The summaries of tolerability include all patients who received any study treatment; those who did not receive study treatment are not included in these summaries. The safety population comprised all randomized patients who received at least one treatment dose and was based on the actual treatment received.

11. Ethical consideration

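### No described side-effect record exists for a dosed patient lost before month 3, although the tolerability summary covers everyone dosed; the week 6 and 18 calls could supply one

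*Combined protocol and SAP*

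**What the plan says.** Tolerability is in the title, is specific objective (d) in section 6, and comes first under the secondary outcomes measures in section 9. Research question (b) in section 5 goes further: "Are oral combination of alpha lipoic acid and vitamin B preparations for the treatment of CTS safe".

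Section 9, Study procedure, names the instrument: "A Patient-Reported Questionnaire to monitor any side effects were used to assess the tolerability of the drugs". That sentence is not tied to a time point. For Visits 2 and 3, at 3 and 6 months, the same section adds: "They were also required to fill in the form regarding the side effects of the treatments". Between visits, the investigators "made a phone call and sent reminder message at the 6th and 18th week to ensure compliance, medication adequacy and follow up review".

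Section 10, Safety Analysis, sets the population: "The summaries of tolerability include all patients who received any study treatment", and "The safety population comprised all randomized patients who received at least one treatment dose".

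The only other route for an adverse event in the text is in section 9, under blinding and emergency unblinding. If the code is broken to manage an event, the medical monitor writes a report that is attached to the case report form.

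The text describes no early-termination visit, no contact with patients who miss a visit, no recording of why a patient stopped, and no rule for a dosed patient without a form.

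**The concern.** The denominator is everyone dosed, but the described source of on-treatment events is a form completed at two visits. A patient lost before the first of these stays in the denominator with no described way to enter the numerator. Patients who leave because of a side effect are the ones a tolerability summary most needs to count, and the number who stopped for that reason cannot be reported from what is collected. With 38 patients planned per arm, a few missing forms can move the observed rate noticeably.

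**Working it through.** **Inputs.** From the documents: 38 patients per arm (section 9, Sample size estimation), 1:1 allocation, treatment for 6 months, forms at months 3 and 6, calls at weeks 6 and 18. I read both visit times as counted from the start of treatment. The documents give no dropout rate and no side-effect rate, so those below are assumptions.

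**The plan's own figure.** 2 × 1.27² × (1.96 + 0.84)² / 0.81² = 38.5, or 38.2 with the plan's rounded intermediates, against 38 stated. It is used here only as the denominator; whether its inputs are right is a separate matter.

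**Shortfall in one arm.** Let m be the dosed patients with no form, p their true side-effect rate and q the rate in attenders.

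- True rate = [(38 − m)q + mp] / 38
- Reported rate, if a missing form counts as no event = (38 − m)q / 38
- Shortfall = mp / 38, which does not depend on q

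Smallest case in the assumed range: 2 × 0.10 / 38 = 0.5 percentage points. Largest: 8 × 1.00 / 38 = 21.1 points.

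With q = 10%, for illustration:

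| m | Reported | True, p = 10% | True, p = 50% | True, p = 100% |
|---|---|---|---|---|
| 2 | 9.5% | 10.0% | 12.1% | 14.7% |
| 4 | 8.9% | 10.0% | 14.2% | 19.5% |
| 8 | 7.9% | 10.0% | 18.4% | 28.9% |

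**If patients without a form were left out instead.** The reported rate is then q, and the error is (m/38)(q − p). With m = 4 and q = 10%, it is (4/38)(0.10 − 0.50) = −4.2 points at p = 50%, zero at p = 10%, and (4/38)(0.10) = +1.1 points at p = 0. The direction then depends on whether non-attenders had more side effects than attenders. This handling would also depart from the stated all-dosed population.

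**Between arms.** If missing forms count as no event, the difference (active minus placebo) is shifted by −(m_A p_A − m_P p_P)/38. With 4 non-attenders at 50% in each arm the shift is zero. With 4 on active and 2 on placebo, both at 50%, it is −(2 − 1)/38 = −2.6 points, in the product's favour. With the arms reversed it is +2.6 points, against the product.

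**Recall gap.** Taking months 3 and 6 as weeks 13 and 26, forms at visits alone leave gaps of 13 weeks. Adding weeks 6 and 18 gives gaps of 6, 7, 5 and 8 weeks, so the longest falls to 8.

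**The case against.** A reader might infer that the plan is shown to make tolerability look better than it is. The documents do not support that. Safety Analysis says who is in the summaries, not that a missing form counts as no event. What is established is an undescribed record and a missing rule; the bias is conditional.

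A reader might also infer that anyone who stops treatment has no report. Nothing in Study procedure ends visits when treatment stops, so such a patient can still complete the form. The complete gap applies only to someone lost before month 3. Someone lost later has the month 3 form and lacks later events.

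Nor can it be said that side effects are recorded only at these two visits. The questionnaire sentence is not tied to a time, the stated purposes of the calls include a general review at which side effects might come up, and the emergency code-break report does not depend on a visit. The flowchart and the data-collection figure are not shown. These points stand. However, the text does not say that the calls record side effects for the summary, and the code-break route is confined to events where the drug's identity must be known.

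A claim that the error favours the product would need the losses to differ between arms, and the documents give no figures for either arm. How far 38 patients can answer whether the product is safe is a question of precision and would remain with complete recording; it is not part of this point.

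**Conclusion.** The point holds as a gap in recording, with a conditional effect on the results. In the visible text, a dosed patient lost before month 3 has no described side-effect record but remains in the tolerability summary. If missing forms count as no event, each arm's rate is understated whenever a non-attender had an unrecorded side effect. Over the assumed ranges the size runs from negligible to large, and the actual size cannot be computed from the documents. For patients lost after month 3, only those whose first side effect came after that form are missed from a count of patients with any side effect. The efficacy outcomes are unaffected. The conclusion rests on the written procedure and would weaken if the flowchart or figure lists further safety contacts.

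**What to change.** In section 9, Study procedure: complete the same side-effect form by telephone at the existing week 6 and week 18 calls. Attempt it once more when a patient stops treatment or misses a visit, and record the reason for stopping.

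In section 10, Safety Analysis, report for each arm, over all dosed patients:

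- the number with at least one side effect;
- the number who stopped because of one;
- the number with no on-treatment form.

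Give the between-arm difference with a 95% interval, and a sensitivity range for the missing forms. Counting all of them as no event and then all as an event gives a range of width m/38 in each arm, for example 4/38 = 10.5 points.

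The calls cannot reach a patient who no longer answers, so the change narrows the gap without closing it; the count of missing forms and the sensitivity range show what remains. The cost is a few minutes per call and some wording. Recorded side-effect rates will probably rise in both arms.

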The quality of life questionnaires have become of recent interest. Although the BCTQ and VAS score are able to scale functional disability and pain, they are not constructed to determine the quality of life which encompasses emotional and social domains of everyday function. The SF 36 measures two distinct physical and mental dimension. It also can good validity and reproducibility and is useful in our clinical setting (22).

Randomisation

Patients' randomisation is done by an independent statistician using a random number generating programme (www.randomizer.org) into two groups (treatment and placebo) using mixed block randomization technique at the ratio of 1:1 i.e. group A and group B. The independent statistician will then code the treatment and the placebo into group A and group B. The written allocation of assignment for each participant with an identification number (code) was sealed in a brown opaque envelope. This envelope will be opened by the researcher on recruitment of a participant. The key coding to the allocation will be revealed by the independent statistician at the completion of the study. An independent statistician will label the treatment and placebo group as either group 'A' or group 'B'.

The participants are assigned to either treatment or placebo arm in a parallel intervention mode.

The principle of random allocation is employed to assign the participants to an intervention (i.e. treatment) and a control (i.e. placebo arm). To achieve an unbiased comparison group and to have a balanced randomization, permuted block randomization with a varying block size is used for the study. The sample size estimated for the study is 76. Hence, there are 19 blocks with a block size of four participants each and one-to- one allocation ratio is used. Random sequence generation is done with the help of a Research Randomizer, an online random number generator (Urbaniak & Plous, 2014). An external member, who is not directly involved in the study, generates the sequence. To have a strict implementation of the generated random sequence, the concealed allocation is achieved using sequentially numbered, opaque and sealed envelopes (SNOSEs). An aluminium foil is kept inside the envelope to prevent possible chances of deciphering. An external member, who is not directly involved in the study, would prepare the SNOSEs.

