The final code is only known to the statistician and the document will be stored in a secure locked safe. The following information will be recorded during the randomization; study ID (assigned during the study initiation), investigator password (assigned during the initiation), subjects screening status, date of informed consent signed by subject, subject's ID no (e.g., Last 4 digits of IC), upon successful randomization, the subjects will be assigned randomization number and treatment. The subject's ID no. and randomization no. will be documented on the Patient Enrolment Log and Patient Identification List.

Blinding and emergency unblinding procedures

The participants and outcome assessor of the study is blinded about the allocation status of the participants. In the setting of an adverse event (AE), for which knowledge of the identity of the test drug is necessary to manage the subject's condition, the sealed emergency code key for that subject may be broken and the test drug identified by the medical monitor. The medical monitor will have a set of sealed emergency code keys (one for each subject) kept in a secured location and he/she will be accessible at all times by telephone. The medical monitor is medical officer who is working in the hospital. He/she is familiar with hospital system and is also aware of the study protocol. Should emergency code key for that subject, identify the test coil and inform the investigator. A detailed report with the date and reason for identifying the study drug will

be prepared by the medical monitor and attached to the case report form. This report must be signed by the medical monitor and the investigator. All unused sealed code keys will be accounted for at the end of the study.

Except in the case of emergency, the treatment blind will be maintained until all subjects have completed the treatment and the database has been cleaned and locked. Any broken code will be clearly justified and explained by a comment on the case report form, along with the date on which the code was broken.

Sample size estimation

Sample size calculation was performed using the study published by Pajardi et al. Sample size was calculated based on improvement to limitations of everyday activity among the patients with CTS as the outcome parameter (1.07 ± 1.27 vs 0.83 ± 0.81). The marginal error (α) was set at 0.05.

Sample size: $2 \frac{\text{SD}^2(2\alpha/2 + Z\beta)^2}{d^2}$

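### The plan claims mixed, varying block sizes but specifies 19 blocks of four, which fill all 76 places; the block rule needs one statement, and the plan should say whether group letters are visible

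*Combined protocol and SAP*

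**What the plan says.** All the block statements are in section 9 of the combined protocol and SAP, under Randomisation. The section opens by allocating patients "using mixed block randomization technique at the ratio of 1:1", to group A or group B. Further on it says that "permuted block randomization with a varying block size is used for the study". Shortly afterwards, having given the sample size as 76, it says: "Hence, there are 19 blocks with a block size of four participants each".

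On coding and concealment, the same section says: "The independent statistician will then code the treatment and the placebo into group A and group B". It continues: "The written allocation of assignment for each participant with an identification number (code) was sealed in a brown opaque envelope", and "This envelope will be opened by the researcher on recruitment of a participant". The envelopes are sequentially numbered, opaque and foil-lined. The key is to be revealed when the study is complete. "The final code is only known to the statistician", and on successful randomisation "the subjects will be assigned randomization number and treatment".

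Under Blinding and emergency unblinding procedures, the medical monitor holds one sealed emergency key per subject. After a break, the monitor identifies the test product and informs the investigator. Outside an emergency, the blind is kept until the database is locked.

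**The concern.** Randomly varying block sizes are normally used so that nobody who knows the method can work out the end of a block from its beginning. The plan claims that protection and then specifies a scheme without it, and it prints the fixed size in the protocol itself. A reader cannot tell which rule produced the list.

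The second issue is how far a code break reaches. One sealed key per subject is meant to confine a break to that subject. The arms, however, carry one letter each, common to every subject in the arm. If the letter appears on the envelope slip or the bottle, decoding one subject decodes both letters. The plan does not say what the opened envelope or the label shows.

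**Working it through.** **Inputs.** Total 76, or 38 per arm (Sample size estimation, repeated under Randomisation); 19 blocks; block size 4; ratio 1:1; one letter per arm (Randomisation).

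**1. The plan's own figure.** 76 / 4 = 19 with no remainder, and 19 × 4 = 76. The figure reproduces, and 76 − 76 = 0 places remain for a block of any other size.

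The count of 19 could not come from a 4/6 mix. The solutions of 4a + 6b = 76 with at least one six are (a, b) = (16, 2), (13, 4), (10, 6), (7, 8), (4, 10) and (1, 12), giving 18, 17, 16, 15, 14 and 13 blocks. Only 19 fours and no sixes gives 19 blocks. With sizes 2 and 4, the only 19-block solution is again all fours. A three-size mix can reach 19 blocks (one 2, seventeen 4s, one 6: 2 + 68 + 6 = 76), but the plan gives every block the size four.

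**2. Predictability with fixed fours.** Assume an observer who sees all earlier letters in order and knows the size. The six orders of AABB are equally likely.

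- The fourth letter is always certain: 1 per block.
- The third letter is certain when the first two agree, with probability 2/6 = 1/3.
- Certain letters per block: 1 + 1/3 = 1.333. Over 19 blocks: 19 × 1.333 = 25.3 of 76, or 33%.
- The total is 19 + Binomial(19, 1/3): possible range 19 to 38, with 95% of lists between 22 and 29.
- Best-guess success by position: 1/2, then 2/3, then (1/3)(1) + (2/3)(1/2) = 2/3, then 1. The sum is 2.833, and 2.833 / 4 = 70.8%.

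**3. The same observer with varying sizes.** The sizes are drawn at random with equal probability, the observer knows the set but not the order of sizes, and 3000 lists of 76 are simulated.

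| Blocks | Letters certain in advance | Best-guess success |
|---|---|---|
| Fixed 4 | 33.3% | 70.8% |
| 4 and 6 | 5.5% | 69.1% |
| 2 and 4 | 10.9% | 72.1% |

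For 4 and 6, 0.055 × 76 = 4.2 letters. Certainty falls sharply, while average guessing barely changes. Blocks of 2 and 4 give a slightly better guess than fixed fours.

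**4. Balance under 4 and 6.** The mean block size is 5, so an even position ends a block with probability of about 2/5. Otherwise, position 76 falls two places into a four, two into a six or four into a six, each with probability of about 1/5. The chance of a difference of 2 is then 1/3, 2/5 and 2/5 respectively. Overall: (1/5)(1/3 + 2/5 + 2/5) = 22.7%, against 23.3% in simulation. In the other roughly 77% of lists the arms are equal. A 39/37 split is equivalent to 2 × 39 × 37 / 76 = 37.97 per arm instead of 38.

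**5. Reach of a code break.** No rate is needed here. With one letter per arm, learning what one subject's letter means gives the meaning of both letters. If letters are visible, a break reported to the investigator reveals the treatment of every subject whose letter the investigator knows, up to all 76. If only participant-specific numbers are visible, it reveals one.

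**The case against.** The strongest reply is that a predictable letter is not a predictable treatment. The key stays with the statistician until the study is complete, participants and outcome assessor are stated to be blinded, and the blind is kept to database lock. This stands. A reader might infer that a third of treatments could be foreseen at enrolment, or that concealment failed. The documents do not support that: foreseeing a treatment needs visible letters and, besides, an earlier link from letter to product, which the plan provides only through an emergency break.

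A second reply is that varying sizes add little, because best-guess success stays at about 69% to 71%. This also stands for average guessing. It does not hold for certainty, which falls from 33% to about 5%, and it does not remove the contradiction in the text.

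A third is that the envelope may show only a number. The text allows this: it mentions an identification number and later a randomisation number. It also speaks of a written allocation, so a visible letter is possible but not established. That is why the second point is conditional. A reader might go further and infer that the envelope-opening researcher or the treating clinician was unblinded because the blinding statement does not name them. That does not follow. The trial is described as double-blind, and outside an emergency the plan gives neither role a route to the treatment code. The missing list of roles is a reporting gap.

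Finally, the 19 × 4 sentence may be a planning count rather than a description of the list. If so, the list may have varied after all. The text cannot settle this; it shows that the two statements disagree, not which one was carried out.

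**Conclusion.** The contradiction is certain and rests on no assumption: sizes described as mixed and varying, against 19 blocks of four that use all 76 places. As specified, the scheme is fixed-size.

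Its practical weight is minor. The figure of about 25 of 76 letters (33%), against about 5% with blocks of 4 and 6, assumes an observer who sees every letter in order and knows the size or the set of sizes. It concerns letters only. The 1:1 balance and the analysis are not affected.

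The code-break point holds only if the arm letter can be seen on the envelope slip or bottle. In that case the one-key-per-subject rule does not confine a break to one subject. The documents report no break and give no break rate, so they support no estimate of how many treatments would become known.

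**What to change.** **Block rule.** Replace the sentence on 19 blocks of four with one rule: blocks of randomly varying size, 1:1, with the sizes held only by the independent statistician and not disclosed to anyone who recruits. Sizes 4 and 6 are a workable example; 2 and 4 are not an improvement. The cost is one sentence and one new list. The downside is a possible 39/37 split, with negligible loss of power (37.97 against 38 per arm).

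**Labels.** Put only the participant-specific randomisation number, which the plan already assigns, on the envelope slip and the bottle, with no group letter. The numbers should follow no arm-related order, and each emergency key should decode only its own number. The cost is individual labelling for 76 subjects.

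**If the list has already been used.** No new list or labels are needed. Report the block sizes actually used, delete *mixed* and *varying* if all were four, and state what the envelopes and bottles showed. The cost is a short note.

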SD – standard deviation = from previous studies or pilot study $Z\alpha/2 = Z \ 0.05/2 = Z \ 0.025 = 1.96$ (From Z table) at 80 % power at type 1 error of 5 % $Z \beta = Z \ 0.20 = 0/842$ (From Z table) at 80 % power d= effect size = difference between mean value

So, the formula: sample size: $2 \cdot SD^2(1.96 + 0.84)^2$ d^2 SD = 1.27 Za/2 = 1.96 Zb = 0.84 $d^2 = (0.81)^2 = 0.66$ $n = \frac{2(1.27)^2 (1.96 + 0.84)^2}{(0.81)^2}$

= 2 (1.61) (7.84)

0.66

= 38 in each arm (Total 76 patients)

Operational definitions

Primary outcome measure

The primary outcome was the electrodiagnostic improvement of the median nerve on NCS before the before the intervention (visit 1) and at three-months (visit 2) and six- months (visit 3). The NCS parameters that are analysed were:

- 1. Distal sensory latency; DSL (normal value for DSL <3.5ms)
- 2. Sensory nerve action potential; SNAP (normal value for SNAP >2.5 μ V)
- 3. Conduction velocity; CV (normal value for CV >50m/s)
- 4. Distal Motor Latency; DML (normal value for DSL <4ms)
- 5. Compound muscle action potential; CMAP (normal value for CMAP>4.0 mV).

Secondary outcomes measures

- Tolerability and safety of oral combination of alpha lipoic acid and vitamin B preparations
- The improvement of scores in Boston Carpal Tunnel Questionnaires (BCTQ) by the SSS scale prior to the intervention, at 3 months and at 6 months
- The improvement of scores in Boston Carpal Tunnel Questionnaires (BCTQ) by the FSS scale prior to the intervention, at 3 months and at 6 months
- The improvement of pain scores in VAS prior to the intervention, at 3 months and at 6 months
- The improvement of quality of life score SF 36 prior to the intervention, at 3 months and at 6 months

Data collection

[figure not shown]
Protection of human rights is the utmost priority for researchers. We obtain informed consent from all participants in this research. The consent process included giving full and comprehensible information about the research and clear assurance of their voluntary

participation. Beneficence is the essence of concern for the well-being of the participants whereby the risk of harm was the least possible.

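### The sample-size formula uses a cited SD (0.81) as the difference between means (0.24), so 38 per arm lacks the stated 80% power, and the calculation is not for the primary outcome

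*Combined protocol and SAP*

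**What the plan says.** Section 9, Sample size estimation, takes its inputs from one published study and names the outcome it uses: "Sample size was calculated based on improvement to limitations of everyday activity among the patients with CTS". It gives the values "as the outcome parameter (1.07 ± 1.27 vs 0.83 ± 0.81". It sets alpha at 0.05, uses the usual normal-approximation formula for two means at 80% power, and defines its last term: "d= effect size = difference between mean value".

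The numbers then entered are "SD = 1.27 Za/2 = 1.96 Zb = 0.84 $d^2 = (0.81)^2 = 0.66", and the result is "38 in each arm (Total 76 patients". The Randomisation subsection builds on this total: "The sample size estimated for the study is 76. Hence, there are 19 blocks with a block size of four participants each".

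Under Operational definitions, the primary outcome is a different quantity: "The primary outcome was the electrodiagnostic improvement of the median nerve on NCS". Five parameters are listed (DSL, SNAP, CV, DML and CMAP), assessed at visit 1, three months and six months. No effect size or SD is given for any of them.

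**The concern.** The cited means are 1.07 and 0.83, so d as the plan defines it is 0.24. The plan takes its SD of 1.27 from the first ± value. By that same usage, 0.81 is the second group's SD. It appears in the formula as d, and nowhere is it offered as a minimal important difference or a chosen target.

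There is a second, separate gap. Even a correct calculation on everyday activity would say nothing about the power of the nerve conduction (NCS) comparison, which is what the trial is meant to decide.

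This is the plan's only power statement. The error does not bias the treatment estimate or inflate type I error. The harm lies in interpretation. A reader would take a result, above all a non-significant one, as coming from a trial with 80% power, and could not tell what NCS difference 76 patients were able to detect.

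**Working it through.** **Inputs.** From Sample size estimation: means 1.07 and 0.83; SDs 1.27 and 0.81; two-sided alpha 0.05 (z = 1.96); 80% power (z = 0.84). From Randomisation: 1:1 allocation, 76 in total. No dropout allowance is stated.

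**1. The plan's own figure.** n per arm = 2 × SD² × (1.96 + 0.84)² / d².

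- With the plan's rounding: 2 × 1.61 × 7.84 / 0.66 = 38.2, stated as 38.
- Unrounded: 2 × 1.27² × 2.8² / 0.81² = 38.5.

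So the 38 reproduces, but only with d = 0.81.

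**2. The size of the substitution.** 1.07 − 0.83 = 0.24, and 0.81 / 0.24 = 3.375. Because d enters squared, n at a fixed SD is understated by 3.375² = 11.4 times.

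**3. The same formula with d = 0.24.** The plan uses 1.27 for both arms. The root-mean-square of the two cited SDs, √((1.27² + 0.81²)/2) = 1.065, and the smaller SD, 0.81, are shown as alternatives. Power is for a two-sided two-sample t-test with 38 per arm.

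| SD | n per arm, d = 0.24 | Power, d = 0.24 | Power, d = 0.81 |
|---|---|---|---|
| 1.27 | 439.1, so 440 | 12.8% | 78.3% |
| 1.065 | 308.8, so 309 | 16.3% | 90.5% |
| 0.81 | 178.6, so 179 | 24.7% | 99.0% |

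The last column places the fault in the value of d. At SD 1.27 the shortfall from 80% comes only from rounding down and from using z in place of t (40 per arm gives 80.4%).

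One-sided testing does not rescue the figure: it would still need 347, 244 or 141 per arm at the three SDs.

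**4. What 38 per arm can detect on an NCS parameter.** No NCS SD is given, so the answer can only be in SD units. For one parameter at one visit, with one observation per patient, the normal approximation is 2.8 × √(2/38) = 0.64 SD. The t-test (74 degrees of freedom) gives 0.651 SD at 80% power and two-sided 0.05.

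The following variations rest on assumed values and are illustrations, not bounds:

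- **Adjusting for the visit 1 value.** This is possible because an NCS is planned at that visit ("they will be subjected for a nerve conduction study (NCS) to determine the severity of CTS"). The figure is multiplied by √(1 − r²). For r = 0.5, 0.6 and 0.7 it becomes 0.564, 0.521 and 0.465 SD.
- **Alpha 0.01**, as if 0.05 were split over five parameters: 0.802 SD unadjusted.
- **34 evaluable per arm:** 0.690 SD at alpha 0.05 and 0.850 SD at alpha 0.01, both unadjusted.

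**The case against.** The contradiction itself is hard to dispute, but four points can be made against the weight put on it.

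*The error may lie in the citation.* The plan does not say whether the pair is two arms, before and after, or change scores, and the ± values are not labelled. The pair could have been copied wrongly. It is true that the documents cannot exclude this. But the plan defines d as a difference between means and treats the first ± value as an SD, so on its own terms 0.81 is an SD. Reading the values as within-patient changes does not recover 38 either: a one-sample calculation with d = 0.24 needs about 220 patients at SD 1.27 or 155 at SD 1.065.

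*The low power concerns the wrong outcome.* The 13% to 25% figures apply to everyday activity only. Power for the NCS parameters is unknown, not shown to be low. This stands, and those figures must not be quoted as power for the primary outcome.

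*Nothing practical changes.* The protocol gives a study completion date of 30 September 2024, and new wording cannot alter the power of the trial. That is so, but it can stop a false power claim from being carried into the reading of the results.

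*A detectable difference in SD units has limits.* It is not in ms, m/s, µV or mV, and it presumes a t-test where section 10 names no test. It also presumes one observation per patient, although laterality is recorded and the counting of bilateral hands is not described. These limits are real. They are reasons to state the conditions next to the figure, and they do not justify keeping the present claim.

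**Conclusion.** The concern holds. The plan's definition of d and its cited means give 0.24, the formula uses 0.81, and 38 per arm depends entirely on that entry. For the cited difference, the plan's formula requires about 440 per arm at its own SD (309 or 179 at the alternatives), and 38 per arm gives about 13%, 16% or 25% power. Those values assume that the cited SDs apply to a between-arm comparison, which the documents do not say. The contradiction between the definition and the value entered does not need that assumption.

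Independently, the only power statement is for an outcome that is not primary. Whether 76 patients are enough for the NCS parameters cannot be determined from the documents. Because the stated power is wrong as written, the statement has to be corrected.

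**What to change.** Withdraw the worked calculation and the 80% power claim as the basis for 76 patients, and keep 76. Do not simply insert 0.24: the formula would then return about 440 per arm against the 38 stated. Nor is 440 a recommended size, since it does not concern the primary outcome. Check the cited pair against its source before finalising the text. If the pair stands, suitable wording is:

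> The calculation in protocol version 3 entered 0.81, an SD, as the difference between means. The cited difference is 0.24, and 38 per arm does not give 80% power for it. The sample size was not derived from an NCS parameter. With 38 evaluable patients per arm, an unadjusted two-sided 0.05 two-sample t-test has 80% power for a between-arm difference of about 0.65 SD in one NCS parameter at one visit. Baseline adjustment would lower this figure; dropout or multiplicity control over the five parameters would raise it.

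The other detectable differences shown in the check rest on assumed values and are not proposed as protocol text.

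The cost is rewording of the sample-size section. Two phrases elsewhere should be brought into line with it: the reliance on an adequate sample size under Baseline Comparability in section 10, and the description of 76 as an estimated size under Randomisation. No patients are added, and the 19 blocks do not change. The stated power becomes less favourable.
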